2.4 LAPAROSCOPY FOR SURGICAL TREATMENT

Laparoscopic radical hysterectomy was described initially by Canis et al.⁵⁰ and Nezhat et al.⁵¹. Since those initial reports, a number of other groups have published their experiences showing the feasibility and safety of this procedure⁵² ⁵³ ⁵⁴ ⁵⁵ ⁵⁶ ⁵⁷. These reports suggest performing the procedure laparoscopically in no way adversely affects the patient's overall prognosis and survival⁵⁸ ⁵⁹ ⁶⁰ ⁶¹ ⁶² ⁶³. Nevertheless, few long-term data are available on the morbidity of laparoscopic radical hysterectomy and survival after this procedure.

To date, no randomized trials have been completed which directly compare laparoscopic and open radical hysterectomy. The largest series thus far on laparoscopic radical hysterectomy, by Spirtos et al⁶⁴, describes 78 consecutive patients, all with early cervical cancer. In that series, 94% of the procedures were completed laparoscopically. The average operative time was 205 min, and the average blood loss was 225 mL. One patient (1.3%) required a blood transfusion, 3 patients had unintended cystotomies, 2 patients required laparotomy to control bleeding, and 1 patient suffered an ureterovaginal fistula. Three patients had microscopically positive or close margins. The authors reported a recurrence rate of 5%.

Obermair et al.⁶⁵ reported upon the feasibility and safety of total laparoscopic radical hysterectomy (TLRH) in 55 patients with cervical (39), endometrial (8), vaginal (2), or recurrent colon cancer (1), or severe pelvic endometriosis (5) followed for 3 years. The median total operating time was 210 minutes, and median hospital stay was 5 days. Intraoperative complications included three vascular injuries and one obturator nerve palsy, all of which occurred in the first half of the series. Early postoperative morbidity included deep vein thrombosis, pulmonary embolism, bladder infection and dysfunction, and vaginal fistula. These events occurred less frequently in the second half of the series. Late

Version 4 October 2014 LACC Trial Page 17 of 105 postoperative morbidity consisted of lymphedema, pelvic abscess and lymphocyst formation, pelvic cellulitis, hyperesthesia of the leg, and small bowel obstruction. It was concluded that TLRH carries acceptably low morbidity that can be reduced with experience with the technique.

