6.8 ACCREDITATION OF PARTICIPATING SURGEONS

Participating surgeons are required to be qualified gynecological oncologists with a proven track record in clinical research and hospital privileges to perform abdominal, laparoscopic, or robotic radical hysterectomy and pelvic lymphadenectomy (for cervical or endometrial cancer), radical trachelectomy or radical parametectomy to qualify as a surgeon for this clinical trial.

In order to minimize surgical complications during a surgeon's initial learning phase, participating gynecologic oncologists must provide evidence to the Trial Management Committee (TMC) of a minimal number of 10 documented cases performed as the main surgeon. Cases will be deidentified to protect the patient confidentiality. The details of the information required should include:

- a. age
- b. BMI
- c. stage
- d. OR time
- e. EBL
- f. Length of stay
- g. Intraoperative complications
- h. Postoperative complications (<30 days)
- i. Red blood cell transfusion requirements (intraoperative and postoperative)

In addition, the prospective Principal Investigator of each site should submit at least 1 unedited video/DVD for approval before submitting to their respective IRB. Each video/DVD will be evaluated and judged by the Trial Management Committee based on the criteria below:

- surgeon technique and tissue handling
- competency in identification and dissection of proper anatomical structures and pelvic spaces
- surgical technique with respect to blood loss and prevention of intraoperative injury
- appropriate decision making based on intraoperative findings
- appropriate use of instrumentation for all parts of the procedure

However, if the institution/investigator has published results and outcomes in peer reviewed literature that demonstrates their skill and technique within this area, then they *may* be exempt from providing the above evidence of their skill.

Once the Principal Investigator is accredited at a site, he/she can then judge the competency of local collaborating surgeons in their institution who wish to enroll patients ensuring the above requirement criteria is met.

Surgeons are not required to have prior experience with lymphatic mapping in order to enroll patients on this study, however skill verification is required. Surgeon skill will be confirmed during the first three cases from each institution. These patients will be excluded from the statistical analyses.

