10.0 STATISTICAL ANALYSES

Primary endpoints will be analyzed according to the intention-to-treat principle. However, as this is a non-inferiority design, there is a view by some biostatisticians that, if there are patients who do not receive the allocated treatment (and in fact 'cross-over' to the alternate arm) an analysis by intention to treat will bias the analysis in favour of the alternate hypothesis that the two groups are not inferior. To overcome this issue, a 'per protocol' analysis i.e. only include those patients who were treated according to the protocol would be used. Therefore being a "modified" version of intent to treat analysis as conveyed to the Trial Safety Committee on 1st October 2014.

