10.2 ANALYSIS OF STAGE II (PHASE III STUDY)

Disease-free survival and overall survival curves will be estimated using the Kaplan-Meier method. The primary comparison of survival distributions will be with the logrank test. Secondary analyses will adjust for prognostic factors using appropriate regression models (e.g. Cox proportional hazards model). All measures of efficacy will be compared by an intention-to-treat analysis including all randomized patients. Toxicity will be analyzed by treatment received. Ninety-five percent confidence intervals will be reported for the differences between the treatment arms.

Descriptive statistics for treatment-related adverse events as well as Quality of life (FACT-Cx, SF-12, MDASI, EQ-5D) and subscales (physical well-being, social well-being, emotional well-being, functional well-being, cervical cancer specific well-being and body image scale), will be calculated for each randomization group at each assessment.

Similarly, descriptive statistics will also be calculated for other outcomes, such as pain scores, anxiety and depression scores and analgesic consumption, etc.

Continuous variables will be assessed for normality and equality of variances between groups. Discrete variables (eg. presence/absence of post-operative infection) will be summarized by frequencies/proportions.

For continuous variables, analysis of variance and/or regression will be used, where appropriate. If assumptions for these tests are violated, alternative non-parametric tests will be used. Difference between groups with respect to discrete variables will be evaluated by using chi-squared tests.

Exploratory analyses adjusting for prognostic factors including age, tumor size, stage, grade of differentiation, depth of myometrial invasion, lymph node involvement, type of treatment, and ECOG status will be performed using proportional hazards regression methods. The impact of baseline QoL on survival will also be investigated.

Provided sufficient patient numbers, outcomes in regards to treatment costs will be analyzed country-specific by the individual investigator of that country.

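### Sections 10.0 and 10.2 conflict on the primary analysis set: ITT, or a per-protocol set mislabelled as modified ITT, with no statement of which decides equivalence

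*Protocol*

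**What the plan says.** Three statements in the protocol bear on the set for the primary comparison.

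- Section 10.0 opens with: "Primary endpoints will be analyzed according to the intention-to-treat principle".
- The same paragraph then reports a view that, when patients cross over to the other arm, ITT favours a finding of non-inferiority. As the way to overcome this it offers a per-protocol analysis: "only include those patients who were treated according to the protocol would be used". It ends by describing this as a modified "version of intent to treat analysis as conveyed to the Trial Safety Committee on 1st October 2014".
- Section 10.2, on the phase III analysis, says: "All measures of efficacy will be compared by an intention-to-treat analysis including all randomized patients".

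The claim that rests on this set is in section 9.0: the procedures are equivalent if disease-free survival (DFS) at 4.5 years differs by no more than 7 points.

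**The concern.** The two sections cannot both be followed as written. Section 10.2 includes every randomised woman. The per-protocol text in 10.0 includes only those treated according to the protocol and presents this as the remedy for a fault in ITT. It does not say whether the per-protocol result replaces ITT, accompanies it or must agree with it. Calling it a modified ITT hides the difference, because selection on treatment received is what ITT rules out.

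This is more than detail left to a statistical analysis plan. The protocol names the set, contradicts itself and mislabels it, so an analysis plan following either section could claim to comply. The trial's one primary claim is equivalence. If the two sets disagreed, the deciding set could be chosen after the results were known. A per-protocol set standing alone would also rest the claim on exclusions made after surgery, which may be related to prognosis and may differ between arms.

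**Working it through.** **1. The plan's own figure.** Section 9.0 gives 740 patients (370 per arm), 90% DFS, a sample-size margin of 7.2 points, 80% power and 95% confidence. Treat 4.5-year DFS as binary and require the 95% CI to lie within ±7.2 points:

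- n per arm = 2(0.9)(0.1)(1.960 + 1.282)² / 0.072² ≈ 365, or 730 in total.
- At 370 per arm, SE = √(0.18/370) = 0.0221. Power = 2Φ(0.072/0.0221 − 1.96) − 1 = 80.8%.

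The stated 740 is reproduced within 3%. The point does not rest on a sample-size error. The figure assumes that all 740 are analysed.

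**2. Which departures could be one-sided.** Conversion to laparotomy can occur only in the TLRH/TRRH arm; section 6.0 asks for its reasons to be recorded there. Abandoning the hysterectomy for positive nodes is written the same way for both arms in 6.1 and 6.2. Conversion is therefore the departure to examine.

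**3. Conversion rates in the series cited in section 2.4.**

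- 78-patient series: "94% of the procedures were completed laparoscopically", so about 6% were not.
- 19-patient series: 2 conversions, 2/19 = 10.5%.
- A further series: no conversions, 0%.

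On 370 women, 6% is 22 and 10.5% is 39.

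**4. Shift if all converted women were dropped.** Let c be the share converted and f their failure rate, and let the other women fail at 10% (from the 90% DFS in 9.0). ITT failure in the arm is 0.10 + c(f − 0.10), and per-protocol failure is 0.10. The arm therefore looks better by c(f − 0.10).

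| f (assumed) | c = 0% | c = 6% | c = 10.5% |
|---|---|---|---|
| 10% | 0 | 0 | 0 |
| 15% | 0 | 0.3 | 0.5 |
| 20% | 0 | 0.6 | 1.1 |
| 25% | 0 | 0.9 | 1.6 |

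Entries are percentage points. The largest, 1.6, is about 23% of the 7-point margin (1.58/7).

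**5. Scale.** With 370 per arm the 95% CI half-width is 1.96 × 0.0221 = 4.3 points. To keep the interval within ±7, the observed difference must lie within about 7 − 4.3 = 2.7 points of zero. A shift of 0.9 to 1.6 points is a material part of that room, but does not by itself show that a conclusion would reverse.

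**The case against.** **ITT is the dominant instruction.** It opens 10.0, it is repeated in 10.2, and 6.7 also uses it for adjuvant-treatment data. The per-protocol text is conditional on patients not receiving their allocated treatment, and can be read as an added analysis. The worry about ITT in non-inferiority trials is a recognised one, and a detailed per-protocol definition is commonly left to the analysis plan. Much of this stands: neither having a per-protocol analysis nor leaving its details open is a fault. What remains is that 10.0 offers it as the remedy for ITT, labels it a form of ITT and gives no order between the two.

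**The shift rests on assumptions.** This also stands. The protocol does not say that conversion is a departure. The reasons for conversion given in 2.4 are bleeding and a cystotomy, so a link with prognosis is assumed. The 10.5% comes from 19 patients, and the range starts at zero.

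A reader might draw two stronger inferences.

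*That abandoned operations would be removed.* Sections 6.1 and 6.2 direct abandonment for positive nodes in both arms, so these women can count as treated according to the protocol. Section 6.0 leaves the decision to the physician, so these passages need reconciling before the set is defined. No one-sided removal follows from them.

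*That 6.8 creates a third primary set.* It says of the first three cases at each institution: "These patients will be excluded from the statistical analyses". But that paragraph opens with "Surgeons are not required to have prior experience with lymphatic mapping in order to enroll patients on this study, however skill verification is required", and the text after it concerns the mapping portion of those cases. Mapping has its own analysis in 10.3. The natural reading is exclusion from that analysis only. Selection would also follow case order and not prognosis, so no loss of power for DFS should be inferred.

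**Conclusion.** Wrong as written. The protocol gives two incompatible instructions for the set that decides its primary claim, and one carries a label that does not describe it. This conclusion follows from the text alone and needs no assumption.

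The possible size is 0 to 1.6 points in favour of TLRH/TRRH, against a 7-point margin. It holds only if per-protocol replaced ITT, if conversions counted as departures, if 0 to 10.5% of that arm were converted, and if converted women failed at 25% against 10% for the rest. The 25% is an assumption; at 10% there is no shift. A reader might go further and infer that the two sets would give opposite conclusions. That is possible, but these figures do not show it.

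**What to change.** In sections 10.0 and 10.2, state the following:

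- The primary analysis is by ITT, with all randomised patients in the arm to which they were allocated.
- A per-protocol analysis is also done.
- Equivalence is claimed only if the 95% CI lies within the margin under ITT and the per-protocol result supports it.
- The per-protocol set is defined before data review. Converted operations and protocol-directed abandonments stay in their allocated arm.

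Delete the sentence calling the per-protocol set a modified ITT.

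As a minor clarification, limit the first-three-cases exclusion in 6.8 to the lymphatic-mapping analysis in 10.3.

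The cost is wording, one more analysis and a slightly stricter success criterion. If support were taken to mean a 95% CI within 7.2 points, the step 1 method gives power in the per-protocol set of 77.8% with 5% of each arm excluded and 74.4% with 10%, against 80.8% with none. Keeping conversions and directed abandonments in the set should hold exclusions down. Making ITT primary and per-protocol a sensitivity analysis would also end the contradiction, but would do less for the bias that 10.0 itself raises.

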10.1 ANALYSIS OF STAGE 1 (FEASIBILITY PILOT)

After the accrual of 100 patients, data will be analyzed to allow determination of several key components of the study which are not the primary endpoints specified in the protocol. These will include:

- Rate of accrual
- Compliance with randomized treatment allocation

Consideration to stopping the study after 100 patients have been accrued will be given if:

- 1. Annual patient accrual is less than 30;
- 2. Less than 75% of patients are available for follow-up
- There is an unacceptable rate of the incidence of complications (>8%) in the TLRH/TRRH group

If these components are satisfied, the Trial Management Committee will make a decision to proceed to the second stage of the complement of 740 patients.

10.2 ANALYSIS OF STAGE II (PHASE III STUDY)

Disease-free survival and overall survival curves will be estimated using the Kaplan-Meier method. The primary comparison of survival distributions will be with the logrank test. Secondary analyses will adjust for prognostic factors using appropriate regression models (e.g. Cox proportional hazards model). All measures of efficacy will be compared by an intention-to-treat analysis including all randomized patients. Toxicity will be analyzed by treatment received. Ninety-five percent confidence intervals will be reported for the differences between the treatment arms.

Descriptive statistics for treatment-related adverse events as well as Quality of life (FACT-Cx, SF-12, MDASI, EQ-5D) and subscales (physical well-being, social well-being, emotional well-being, functional well-being, cervical cancer specific well-being and body image scale), will be calculated for each randomization group at each assessment.

Similarly, descriptive statistics will also be calculated for other outcomes, such as pain scores, anxiety and depression scores and analgesic consumption, etc.

Continuous variables will be assessed for normality and equality of variances between groups. Discrete variables (eg. presence/absence of post-operative infection) will be summarized by frequencies/proportions.

For continuous variables, analysis of variance and/or regression will be used, where appropriate. If assumptions for these tests are violated, alternative non-parametric tests will be used. Difference between groups with respect to discrete variables will be evaluated by using chi-squared tests.

Exploratory analyses adjusting for prognostic factors including age, tumor size, stage, grade of differentiation, depth of myometrial invasion, lymph node involvement, type of treatment, and ECOG status will be performed using proportional hazards regression methods. The impact of baseline QoL on survival will also be investigated.

Provided sufficient patient numbers, outcomes in regards to treatment costs will be analyzed country-specific by the individual investigator of that country.

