5.0 STUDY DESIGN

This Phase III international, multi-centre, open-label, randomized clinical trial design is an equivalence study with the hypothesis that TARH is equivalent TLRH in terms of disease free survival (DFS). The study will be conducted in two stages.

5.1 STAGE 1

The first stage will assess feasibility of recruitment and delivery of the intervention and collect quality of life on the first 100 patients.

5.2 STAGE 2

The Trial Management Committee (refer to Section 19.2) will decide whether the trial will progress along Option 1 or Option 2 based on clinical and economical feasibility and the level of interest amongst the clinical community.

[figure not shown]
Option 1

A randomized equivalence trial with disease-free survival as the endpoint is the definitive means of determining whether TLRH is at least equivalent to TARH. As such, it is planned to extend the trial to a larger randomized equivalence clinical trial (additional 640 patients) assessing disease free survival at 4.5 years from surgery.

Option 2

The study will follow-up the cohort of patients who had received a total laparoscopic or robotic radical hysterectomy for a minimum of 4.5 years post-surgery to determine whether the estimate of disease-free survival for patients who undergo laparoscopic or robotic surgery is consistent with the (control group) four-year disease-free survival rate of 90%.

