8.0 RANDOMISATION

All eligible patients will be required to provide informed signed consent before being randomized. Prior to randomization, each patient will be screened for eligibility according to the inclusion and exclusion criteria. A web-based computer randomization procedure will be coordinated centrally from Australia.

Randomization will be performed using the method of minimization with an equal allocation between the two treatment groups. Randomizations will be stratified according to treating centre, and disease stage as determined clinically according to the current FIGO guidelines and patient's age (≤ 70 and > 70 years).

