9.0 SAMPLE SIZE

The primary objective of this study is to determine whether Total Laparoscopic (TLRH) or Robotic Radical Hysterectomy (TRRH) is equivalent to Total Abdominal Radical Hysterectomy (TARH) with respect to 4.5 year disease free survival. If the disease free survival does not differ by more than 7% then the two procedures will be considered to be equivalent.

The 4.5 year disease free survival rate for patients undergoing TARH is estimated to be 90%. The following table, based on exponential survival times, gives the sample sizes required for levels of differences in disease free survival rates at 4.5 years. These differences will be regarded as being equivalent based on different accrual and follow-up times. The sample sizes assume a power of 80%, 95% confidence and two-tailed comparisons.

Based on these numbers, for a 4.5-year accrual and 4.5-year follow-up, a total of 740 patients (370 per arm) would be sufficient to declare equivalence with an equivalence margin of 7.2% or less at 4.5 years. If accrual is sufficiently rapid (ie less than 4.5 years), consideration will be given to increasing the sample size to reduce the amount of follow-up required but maintain the equivalence margin. This sample size will have 87% power to detect a non-inferiority margin of the same magnitude.

Table for Option 1 Randomised Design

| 4yr Disease Free Survival difference to be regarded as equivalent | | Years | Total Sample Size | |
|-------------------------------------------------------------------|------|---------|-------------------|------|
| TLRH/TRRH | TARH | Accrual | Follow-up | |
| | | 3 | 3 | 1660 |
| | | 3 | 4 | 1380 |
| 85 | 90 | 3 | 5 | 1190 |
| | | 4 | 4 | 1280 |
| | | 4 | 5 | 1114 |
| | 90 | 3 | 3 | 750 |
| | | 3 | 4 | 760 |
| 84 | | 3 | 5 | 654 |
| 04 | | 4.5 | 4.5 | 740 |
| | | 4 | 5 | 614 |
| | | 5 | 4 | 656 |
| | | 3 | 3 | 794 |
| | | 3 | 4 | 660 |
| 85 | 92 | 3 | 5 56 | |
| | | 4 | 4 | 612 |
| | | 4 | 5 | 532 |

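### The named primary test is a logrank test of no difference, and nothing in the protocol ties it, or the planned 95% confidence interval, to the equivalence margin

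*Protocol*

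**What the plan says.** - **Design.** Section 5.0 says that the "design is an equivalence study with the hypothesis that TARH is equivalent TLRH". Section 7.1 defines the primary outcome as treatment equivalence, judged by DFS at 4.5 years after surgery. Section 10.0 describes the trial differently: "However, as this is a non-inferiority design, there is a view by some biostatisticians that".
- **Margin.** Section 9.0 gives the rule "If the disease free survival does not differ by more than 7% then the two procedures will be considered to be equivalent". It then says that 740 patients "would be sufficient to declare equivalence with an equivalence margin of 7.2% or less at 4.5 years". The sizes assume 80% power, 95% confidence and two-tailed comparisons, and the same number is credited with 87% power for non-inferiority at the same margin.
- **Analysis.** Section 10.2 says "The primary comparison of survival distributions will be with the logrank test". It adds "Ninety-five percent confidence intervals will be reported for the differences between the treatment arms". It does not compare those intervals with 7% or 7.2%.

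**The concern.** A standard logrank test can reject equality of two survival curves. Failing to reject equality does not show that the curves lie within a margin of each other, because a small or immature data set also fails to reject. Here the design question concerns a margin and the named primary test does not use it. The pieces of a proper criterion are all present (a margin, a confidence level, an interval for the difference), but the sentence that makes them a decision rule is missing.

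Two teams following this protocol could therefore take the same data and reach opposite primary conclusions. The question is whether minimally invasive surgery preserves cancer control, so the costly error is to call it equivalent when it is worse by the full margin. The protocol names its primary test itself, so this is not a detail left to a statistical analysis plan. A later plan with an interval rule would have to override the protocol.

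**Working it through.** **Inputs.** From section 9.0: control DFS 90% at 4.5 years, 370 per arm, accrual 4.5 years and follow-up 4.5 years, exponential survival, margin 7% or 7.2%, 95% confidence. From section 12.4: scheduled visits end at month 54. No dropout is stated, so none is assumed.

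**1. The plan's own figure.** Two one-sided tests at 0.025 each, both arms at 90%, on the 4.5-year proportions:
- n per arm = 2 × 0.9 × 0.1 × (1.960 + 1.282)² / margin².
- Margin 7.2%: 365 per arm, 730 in total, close to the stated 740. Margin 7.0%: 386 per arm, 772 in total.
- With 370 per arm, SE = √(0.18/370) = 0.0221. Equivalence power = 2Φ(margin/SE − 1.960) − 1, which is 80.8% at 7.2% and 77.5% at 7.0%. Non-inferiority power is 90.4% and 88.8%.

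So 740 agrees with a rule in which the 95% interval must lie inside 7.2%. Section 9.0 mentions exponential survival. On the log-hazard scale at 7.2%, non-inferiority power is 85.7% (87% is stated), and the two one-sided tests would need about 848.

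**2. Logrank when the truth is 83% versus 90%.**
- Hazards: −ln(0.90)/4.5 = 0.0234 and −ln(0.83)/4.5 = 0.0414. Hazard ratio 1.768, logarithm 0.570.
- Expected test statistic with D events: (√D / 2) × 0.570. P(non-significant) = 1 − Φ(statistic − 1.960).
- Everyone censored at 4.5 years: D = 370 × 0.10 + 370 × 0.17 = 99.9, statistic 2.85, P = 18.7%.
- Everyone followed to study end: event probability 1 − [exp(−4.5λ) − exp(−9λ)]/(4.5λ), which is 0.146 and 0.243. D = 370 × 0.389 ≈ 144, statistic 3.42, P = 7.2%.

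**3. The 7% rule in the same situation.**
- Read as a rule on the point estimate: the estimate is centred on the limit, so it passes about 50% of the time.
- Read as a rule on the 95% confidence limit: it passes 2.5% of the time.

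**4. Results on which the readings disagree.** Take observed control DFS of 90% and an observed deficit d, with SE(d) = √{[0.09 + (0.9 − d)(0.1 + d)]/370}. A Wald test on the difference stands in for the logrank.
- d + 1.96 SE(d) reaches 7 points from d of about 2.5 points upward.
- d stays below 1.96 SE(d) up to about 4.7 points.
- Between those values the result is non-significant and inside the 7% rule read on the estimate, yet the 95% interval still includes a 7-point deficit.
- Example: 90% versus 85.5%. d = 4.5 points, SE = 2.40 points, z = 1.87, 95% interval −0.2 to 9.2 points.

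**The case against.** The best defence is that section 9.0 already implies an interval rule. It states 95% confidence, a margin and two-tailed comparisons, and 740 is close to what such a rule requires. Section 10.2 promises the interval for the difference, so the data needed to judge the margin would be reported. All of this is correct. It makes the point-estimate reading only one interpretation, and the 50% figure applies only under that reading. It does not supply the missing link, because section 10.2 still gives primacy to a test that makes no use of the margin.

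Three stronger readings are tempting, and the protocol does not support them.
- A reader might infer that the protocol declares equivalence from a non-significant logrank. It nowhere says so; it only leaves that possibility open.
- A reader might infer that the trial cannot answer its primary question. It can, if the reported interval is set against a margin; what is lacking is the rule that says so.
- A reader might infer that the primary test is unstratified and ignores the minimisation factors. Section 8.0 says "Randomizations will be stratified according to treating centre, and disease stage", with age also listed, and section 10.2 simply does not say whether the logrank is stratified. That detail may properly sit in a statistical analysis plan.

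It is also fair to object that the logrank would usually detect a true 7-point deficit. If women are followed to study end it misses one in only about 7% of trials. That is still nearly three times 2.5%, and the visit schedule, which stops at month 54, points toward the higher figure.

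**Conclusion.** The point holds: the named primary comparison does not address the margin-based hypothesis, and no other sentence fixes how the margin is to be judged. If non-significance were taken as equivalence, a true 7-point deficit would pass in about 7% to 19% of trials. The intended level is 2.5%.

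The sizes assume exponential survival, control DFS of 90%, 370 per arm and no dropout. Fewer events would raise the logrank figures: at half of the 144 events, about 32% of trials would be non-significant. The conclusion itself rests on the wording of sections 5.0, 7.1, 9.0, 10.0 and 10.2 and does not depend on these figures.

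**What to change.** In section 10.2, replace the logrank sentence with a primary criterion: the difference in Kaplan-Meier 4.5-year DFS (TLRH/TRRH minus TARH) with its two-sided 95% confidence interval, compared with one pre-stated margin. Equivalence requires the whole interval to lie within plus or minus the margin. Non-inferiority requires the lower limit to lie above minus the margin. Keep the logrank test and the Cox hazard ratio as supportive analyses.

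Three related edits are needed for the rule to be complete:
- State whether equivalence (section 5.0) or non-inferiority (section 10.0) is the primary claim.
- Reconcile 7% with 7.2%. On the 4.5-year proportions, 740 patients give equivalence power of about 81% at 7.2% and about 78% at 7.0%.
- Reword the 7% sentence in section 9.0 so that it refers to the confidence interval.

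The cost is a protocol amendment in wording. No new data are required. On the proportion calculation 740 supports the rule at 7.2%; choosing 7.0% means accepting slightly lower power or recruiting about 772.
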